**Table 5.2-1 Study drug kit labels**

Affixed to Drug Product Kit	For Pharmacy Log
Subject ID# _____ Date _____ T2R-002 Study TREATMENT KIT#: XXXX GLS-1200 / Placebo 7 ml (#28 vials) Site #101 Uinversity of Pennsylvania [name] Store between 2-25°C (Refrigerated or Room Temp) Expiration Date: MM YYYY Packaged at the University of Pennsylvania, Philadelphia, PA For Investigational Use Only	Subject ID# _____ Date _____ T2R-002 Study TREATMENT KIT#: XXXX GLS-1200 / Placebo 7 ml (#28 vials) Site #101 Uinversity of Pennsylvania [name] Store between 2-25°C (Refrigerated or Room Temp) Expiration Date: MM YYYY Packaged at the University of Pennsylvania, Philadelphia, PA For Investigational Use Only  ACTIVE / PLACEBO

## 5.3 Handling of Study Drug

Study drug will be stored between 2°C and 25°C in the University of Pennsylvania Investigational Drug Service. Investigational product must be stored in a secure area according to local regulations.

#### **5.4 Dispensing of Study Drug**

It is the responsibility of the Investigators that study drug is dispensed only to study participants. Authorized personnel are the only ones to dispense product according to local regulation.

At enrollment, study participants will be provided one kit containing 28 vials of study drug, 28 nasal atomizers, and 84 syringes. Each vial and atomizer will be used for single-day drug administration and then discarded, while a new syringe will be used at each of the three daily administrations and then discarded.

The study pharmacist or study coordinator will demonstrate to participants how to remove drug from the vial into syringes and to self-administer product. Coordinator will also review proper handling and storage conditions for the materials provided. A link will be provided to an instructional video on study drug handling and administration.

#### **5.5 Precautions with Investigational Medicinal Product**

Participants will be instructed to keep all unused study drug either refrigerated or at room temperature. Participants will be instructed to keep in-use vials refrigerated at 2-8°C.

#### **5.6 Preparation of Investigational Product**

Study product will be supplied in “ready to use” daily-use vials. Sufficient atomizers, vial adapters and syringes will be provided.

#### **5.7 Record of Investigational Product Disposition at Site**

It is the responsibility of the Investigator to ensure that a current record of investigational product disposition is maintained at each study site where investigational product is inventoried and disposed. Records or logs must comply with applicable regulations and guidelines, and should include:

- Amount received and placed in storage area;
- Amount currently in storage area;
- Label ID number or batch number and use date or expiry date;
- Dates and initials of person responsible for each investigational product inventory entry/movement;
- Amount dispensed to each participant, including unique participant identifiers;
- Amount transferred to another area/site for dispensing or storage;
- Amount destroyed, if applicable

#### **5.8 Return and Destruction of Investigational Product**

Subjects will discard that day's study drug vial after the third daily dose.

#### **5.9 Device Accountability**

The pharmacy will maintain a log to track the lot numbers and distribution of the atomizer used in the study, LMA® MAD NASAL™ Intranasal Mucosal Atomization Device. Participants can discard syringes after dosing both nostrils at each time point and can discard the atomizer after the third daily dose. Unused devices (if applicable) can be discarded at completion of study treatment period.

---

## 6. STUDY PROCEDURES AND TREATMENTS

### 6.1 Procedures by Visit (also see Table S2)

#### 6.1.1 Day 0: Review Study and Eligibility Criteria; Obtain Informed Consent, Enrollment

Subjects will be recruited and provided the informed consent for review. Study staff will review the protocol with the prospective participant and obtain written informed consent. One copy of the informed consent will be maintained at the site, and the other given to the participant.

Study procedures that will be completed include:

- Review medical history, demographics
- Review concomitant medications
- Perform physical exam, height, weight, vital signs
- Perform study ECG, provide order for baseline safety labs (CBC and Basic Metabolic Profile)
- Perform baseline nasopharyngeal swab for viral PCR
- Collect serum for viral antibodies
- Collect saliva for TAS2R genotyping (collection of saliva for genetic testing is optional)
- Provide instruction on self-administration of study drug and device
- Provide study diary

#### 6.1.2 Week 2: intermediate visit

Two weeks into the study participants will return to the study site to complete the following study procedures:

- Review study drug self-administration
- Review new concomitant medications
- Review adverse effects, any new diagnosis of SARS-CoV-2 infection
- Review study diary
- Perform targeted physical exam
- Perform nasopharyngeal swab for viral PCR
- Collect serum for viral antibodies
- Collect plasma for quinine measurement

#### 6.1.3 Week 4: end of treatment

Study procedures that will be completed include:

- Review new concomitant medications
- Review adverse effects, any new diagnosis of SARS-CoV-2 infection
- Perform targeted Physical exam
- Review study diary
- Perform nasopharyngeal swab for viral PCR
- Perform ECG
- Perform repeat safety labs (CBC and Basic Metabolic Profile)
- Collect serum for viral antibodies

#### 6.1.4 Week 6: follow up visit

Study procedures that will be completed include:

- Review new concomitant medications
- Review adverse effects, any new diagnosis of SARS-CoV-2 infection

---

- Review and collect study diary
- Perform targeted physical exam
- Perform nasopharyngeal swab for viral PCR
- Collect serum for viral antibodies
- Collect and review diary

## 6.2 Timing and Evaluations

### 6.2.1 Informed Consent (Day 0)

Study personnel will meet with prospective study participants, explain the study, and provide them with an informed consent form (ICF) that describes the eligibility criteria for entering the study, study treatments and follow-up procedures. An informed consent must be signed prior to any study related procedures being performed. A copy of the signed and dated consent form will be given to the participant.

### 6.2.2 Enrollment (Day 0)

Participants who consent to be in the study will be assigned a unique participant identification designation number (PID#). Once assigned, PID numbers cannot be reused for any reason. Information regarding participant's PID# and screen date will also be documented on a screening log. See section 8.7 for allocation schedule and process.

#### *Medical History*

Investigators should document all significant illnesses that the participant has experienced as Medical History in the last 6 months. Illnesses' first occurring or detected during the study and/or worsening of an existing illness that occurs after the first administration of study drug are documented as AEs on the electronic case report form (eCRF).

#### *Prior and Concomitant medications*

Prior treatments, defined as administered up to 8 weeks prior to the time of informed consent, will be recorded in the eCRF as prior medications. Concomitant treatments, defined as continuing or new treatments taken at or after the signing of the informed consent, will be recorded in the eCRF as concomitant medications.

#### *Review of study drug self-administration*

Study staff will review with the participant the procedures for self-administration and provide a link for an instructional video.

#### *Provide study drug and diary*

Study staff will provide participants with a kit containing study drug, syringes, and atomizers for 28 days of treatment. A study diary will be provided and instructions on how to complete the diary will be reviewed.

### 6.2.3 Safety Assessments

#### 6.2.3.1 Adverse effects

Adverse effects will be queried at the Week 2, 4, and 6 visits.

**6.2.3.2 Physical Assessments and Targeted Physical Assessment**

A physical examination will be performed at study enrollment and a targeted physical examination will be performed at the Week 2, 4 and 6 visits and any unscheduled visit.

**6.2.3.3 Vital Signs**

Participant vital signs will be performed at all study visits.

**6.2.3.4 Weight and Height**

Participant height and weight will be assessed and recorded at enrollment.

**6.2.3.5 12-lead ECG**

A 12-lead ECG will be performed at enrollment and at the Week 4 visit.

**6.2.3.6 Safety Laboratory Evaluations**

Blood draws for a complete blood count with differential and a basic metabolic panel (consisting of sodium, chloride, potassium, bicarbonate (CO2), blood urea nitrogen (BUN), creatinine, and glucose) will be performed at baseline and at the Week 4 visit.

**6.3 Assessment of Laboratory Abnormalities**

Serum chemistries (basic metabolic panel) and complete blood count with differential blood count will be graded as noted in Section 7.1.

**6.4 Assessment of Clinical Adverse Events**

Participants will also be queried regarding the occurrence of any adverse events, concomitant medications and new onset disease during their clinic visits. Participants will be reminded to contact study personnel and immediately report any event that may happen for the duration of the study up to and including the final study visit. Events will be recorded in eCRF.

The Investigator will grade clinical AEs (based on discussions with study participants) using the NCI Common Terminology Criteria for Adverse Events v5.0. Laboratory abnormalities of grade 2 or higher will be captured.

**6.5 Nasopharyngeal swab PCR for presence of SARS-CoV-2 virus**

Nasopharyngeal swabs will be performed at baseline and Weeks 2, 4 and 6 to perform PCR to document the presence of SARS-CoV-2 virus RNA, which may be done by research use only (RUO) assays.

**Results of the Nasopharyngeal Swab**

Results of the nasopharyngeal swab may be received as soon as one day after testing.

If the PCR results are positive for SARS-CoV-2 infection at enrollment, the participant will be asked to remain in the study, administer study drug as per protocol, comply with all required testing for safety, and complete the remaining visits. If the participant does not want to administer study drug or complete testing, they will be asked to consent to telephone contact for the remaining visits.

**6.6 Serum for SARS-CoV-2 antibodies**

Serum will be collected at baseline and Weeks 2, 4 and 6 to measure SARS-CoV-2 antibodies using RUO assays.

## **6.7 Definition of confirmed SARS-CoV-2 infection and SARS-CoV-2 symptom score**

Participants will be queried as to any new diagnosis of SARS-CoV-2 infection, defined as a positive PCR test for SARS-CoV-2. This definition is consistent with the current protocol for viral PCR testing. All deaths will be considered as treatment failures.

Participants will also be instructed to maintain a symptom diary that includes those symptoms considered common for SARS-CoV-2. The diary is inclusive of symptoms identified by the World Health Organization for a diagnosis of SARS-CoV-2 as well as more recently identified symptoms such as conjunctivitis, diarrhea, and loss of taste or smell. Each symptom will be scored as present (score of 1) or absent (score of 0) for each two week interval and the incidence of each symptom will be summarized by treatment group. In addition, the average number of days subjects had each symptom throughout the study period (6 weeks) will be summarized by treatment group.

## **6.8 Exposures to SARS-CoV-2**

Exposure history to patients known to have SARS-CoV-2 will be included as part of the participant diary.

## **6.9 Saliva for TAS2R genotyping**

Samples of saliva will be collected for genotype analysis of the bitter taste receptors (T2R) using chip technology that includes known common TAS2R single nucleotide polymorphisms (SNPs). Dense genotyping, after purification and quantification of genomic DNA, will interrogate and genotype 96 of the T2R SNPs with high minor allele frequency (mostly missense). The results of genotype analysis of T2Rs that are stimulated by quinine will serve as an exploratory co-variate of treatment outcome and be presented as a descriptive analysis. This data is for study purposes only and will not be entered into the participants' clinical record.

# **7. EVALUATION OF SAFETY AND MANAGEMENT OF TOXICITY**

## **7.1 Safety Parameters**

### **7.1.1 Adverse Events (AEs)**

An adverse event (AE) is defined as any unfavorable and unintended change in the structure, function, or chemistry of the body, or worsening of a pre-existing condition, temporally associated with the use of a product whether or not considered related to the use of the product. In this study, such changes will be monitored, classified, and summarized, as Clinical or Laboratory AEs. Medical conditions/diseases present before starting the investigational drug will be considered adverse events only if they worsen after starting study treatment.

An unexpected AE is:

- Not identified in the Investigator's Brochure (IB) or otherwise not expected from the characteristics of the clinical material
- Not listed at the specificity or severity that has been previously observed

Study related AEs include the following:

- Pre- or post-treatment complications that occur as a result of protocol mandated procedure

- Any pre-existing condition that increases in severity, or changes in nature during or as a consequence of the study drug phase of a human clinical trial, will also be considered an AE
- Complications and termination of pregnancy; see Section 7.1.8 for additional information.
- All AEs that occur after enrollment and throughout the duration of the study will be recorded.

Study related AEs do not include the following:

- Elective medical or surgical procedures
- Non-elective medical or surgical procedures (e.g., surgery, endoscopy, tooth extraction, transfusion) performed; the condition that leads to the procedure is an AE
- Pre-existing diseases or conditions or laboratory abnormalities present or detected before study enrollment that do not worsen
- Situations where an untoward medical occurrence has not occurred (e.g., hospitalization for elective surgery, social and/or convenience admissions).
- Overdose without clinical sequelae
- Any medical condition or clinically significant laboratory abnormality with an onset date before the first dosing and not related to a protocol associated procedure is not an AE. It is considered to be pre-existing and will be documented on the medical history eCRF
- Any laboratory abnormality that is considered as non-significant or considered as related to another non-study related condition
- Uncomplicated pregnancy
- An induced elective abortion to terminate a pregnancy without medical reason

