#### **7.1.6 Abnormal Laboratory Value**

Grade 2 and higher laboratory abnormalities (e.g., serum chemistry, CBC) are to be recorded.

Any laboratory abnormality that is new in onset or worsened in severity or frequency from the baseline condition and meets one of the following criteria will be recorded as an AE:

- Requires therapeutic intervention or diagnostic tests
- Leads to discontinuation of study treatment
- Has accompanying or inducing symptoms or signs
- Is judged by the investigator as clinically significant

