### **7.2 Methods and Timing for Collection and Recording of Safety Data**

At the time of each study visit, participants will be queried as to adverse events that have occurred in the interim period and the current status of any AE that was reported at a prior visit that has not yet resolved. As delineated above, both solicited and non-solicited events will be sought. Additionally, labs and ECGs will be reviewed for safety.

All AEs, regardless of severity, seriousness, or presumed relationship to study treatment, must be recorded using medical terminology in source documents and on the eCRF. Whenever possible, a diagnosis will be documented, in lieu of symptoms. The source document and the eCRF must contain the Investigator's opinion concerning the relationship of the AE to study treatment.

AEs should be described with the following attributes:

- Duration (start and end dates)
- Seriousness
- Severity
- Causality
- Action(s) taken
- Outcome

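### Protocol 7.1.1 lets causal attribution decide whether a laboratory abnormality is an adverse event, against its own AE definition, 7.1.6, 7.2 and SAP 9.1

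*Protocol*

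**What the plan says.** Protocol 7.1.1 defines an AE as an unfavourable, unintended change "temporally associated with the use of a product whether or not considered related to the use of the product". SAP 9.1 repeats that definition and attaches no exclusions.

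Later in Protocol 7.1.1 a list opens with "Study related AEs do not include the following". One of its bullets is "Any laboratory abnormality that is considered as non-significant or considered as related to another non-study related condition".

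Protocol 7.1.6 has its own laboratory rules. First, "Grade 2 and higher laboratory abnormalities (e.g., serum chemistry, CBC) are to be recorded". Second, it makes an AE of "Any laboratory abnormality that is new in onset or worsened in severity or frequency from the baseline condition and meets one of the following criteria". The criteria are a need for treatment or diagnostic tests, discontinuation of study treatment, accompanying signs or symptoms, and the investigator's judgement of clinical significance.

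Protocol 7.2 adds: "All AEs, regardless of severity, seriousness, or presumed relationship to study treatment, must be recorded". Causality is one of the attributes that 7.2 asks sites to describe for each AE. Protocol 7.1.5 and SAP 9.1.2 both include a not-related category for recorded events.

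**The concern.** Under one part of 7.1.1 cause is irrelevant to whether something is an AE; under another it is decisive for laboratory findings. A site cannot follow both. If it follows the exclusion, a clinically important laboratory change that the investigator puts down to another illness never becomes an AE record, so the relationship field that should carry that judgement is never filled in. SAP 9.1.2 counts a missing relationship as related, but that safeguard works only on events that have been entered as AEs.

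Safety and tolerability form a primary objective. Protocol 1.4 calls the adverse effects of topical quinine unknown and lists thrombocytopenia as the most common hematologic change with oral quinine. The blood count is scheduled at baseline and once afterwards, at Week 4. The trial studies a viral infection, so an alternative explanation for an abnormal blood count will sometimes be at hand.

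**Working it through.** The documents state no figure on this point to reproduce. The check is a comparison of the text, followed by an illustration of size.

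**Step 1. Does cause affect AE status?**

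| Place | What it does | Does cause matter? |
|---|---|---|
| Protocol 7.1.1 definition; SAP 9.1 | Defines an AE | No |
| Protocol 7.1.1 exclusion bullet | Removes laboratory abnormalities attributed to another condition | Yes |
| Protocol 7.1.6 | Makes a new or worsened abnormality an AE on any one of four criteria | No |
| Protocol 7.2 | Requires every AE to be recorded, with causality described | No |
| Protocol 7.1.5; SAP 9.1.2 and 9.1.5 | Classify and tabulate not-related AEs | No (an attribute only) |

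The exclusion bullet is the only entry that makes cause decisive.

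**Step 2. Does the list's heading confine it to causally related AEs?** The term study related could suggest so, but two features of 7.1.1 count against it. The companion list of what such AEs include ends by covering every AE from enrollment through the study, whatever its cause. And a neighbouring bullet in the exclusion list settles AE status outright: a condition with "onset date before the first dosing and not related to a protocol associated procedure is not an AE". The list therefore works, at least in part, as a definition of what is not an AE.

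**Step 3. What depends on AE status?**
- Treatment-emergent AE tables (SAP 9.1.5): built from AE records.
- Grade 3+ rate and its 95% confidence limit (Protocol 8.3.1): built from AE records.
- Serious AEs (Protocol 7.1.2): defined as AEs that meet a further condition. Section 9.6.2 then requires reporting without regard to cause, but only for events already classed as AEs.
- Events requiring expedited reporting (Protocol 7.3.1): defined among AEs, including Grade 3 or greater laboratory abnormalities, with notice to the sponsor within 24 hours and no relatedness condition.

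Not dependent on AE status: the hematology and chemistry shift tables, mean plots and full listings in SAP 9.2, and the recording of Grade 2+ abnormalities under Protocol 6.4 and 7.1.6. Not changed by the bullet: the 7.3.2 stopping rules, which count only events assessed as related.

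**Step 4. Illustration of size (assumed counts).** Inputs: n = 150 on GLS-1200 and n = 75 on placebo (protocol synopsis, Table S1). The event counts are assumptions, taken as the only Grade 3+ events in the arm. Exact (Clopper-Pearson) 95% limits for x events in n:
- lower = 0.025 quantile of Beta(x, n − x + 1), or 0 when x = 0
- upper = 0.975 quantile of Beta(x + 1, n − x)

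| Arm | Events | Rate | Exact 95% CI |
|---|---|---|---|
| GLS-1200, n = 150 | 0 | 0% | 0 to 2.43% |
| | 1 | 0.67% | 0.02 to 3.66% |
| | 3 | 2.00% | 0.41 to 5.73% |
| | 5 | 3.33% | 1.09 to 7.61% |
| Placebo, n = 75 | 0 | 0% | 0 to 4.80% |
| | 3 | 4.00% | 0.83 to 11.25% |

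If every event in the GLS-1200 arm is attributed elsewhere and left out, the upper limit falls to 2.43% from 3.66% (one event), 5.73% (three) or 7.61% (five). If two of three are left out, it falls from 5.73% to 3.66%. In placebo, leaving out three moves it from 11.25% to 4.80%.

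**The case against.** A reader might infer that blood abnormalities can disappear from the safety tables altogether. The documents do not support that. SAP 9.2 builds shift tables, plots and listings from the laboratory results whatever their AE status, so a low platelet count remains visible by arm. These outputs do not fully replace an AE record: the shift tables show only low, normal or high, and no table in SAP Appendix B reports laboratory grade outside the AE tables.

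A reader might also infer that abnormalities go unrecorded, or that the stopping rules are weakened. Neither follows. Grade 2+ abnormalities are recorded under 6.4 and 7.1.6 with no condition on cause, and every 7.3.2 trigger already requires relatedness. An abnormality attributed elsewhere would not count towards stopping even without this bullet.

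The strongest argument on the other side is that nothing says 7.1.1 overrides 7.1.6. A clinically significant platelet fall meets a 7.1.6 criterion directly, and 7.2 and the SAP point the same way, so a careful site might record it anyway. The heading also permits a narrower reading. This stands as far as it goes: the text is an unresolved conflict, not a clean removal. But nothing says 7.1.6 prevails either, and sites could resolve it differently.

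It is also fair that an intercurrent illness first occurring during the study is itself documented as an AE (Protocol 6.2.2), so the participant would usually still count as having any treatment-emergent AE. The laboratory term and its grade could still be missing.

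Finally, attribution is made blind in both arms. The documents give no basis for claiming a distortion between arms, and none is claimed.

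**Conclusion.** The concern holds as an internal contradiction with a practical consequence. The bullet in 7.1.1 makes AE status depend on causal attribution, contrary to the definition in the same section, 7.1.6, 7.2 and SAP 9.1. The exposed outputs are the treatment-emergent AE tables, the Grade 3+ rate and limit in 8.3.1, serious AE status, and the 24-hour notice.

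The size cannot be stated, because the documents give neither an expected rate of such abnormalities nor the share that would be attributed elsewhere. The intervals above show sensitivity to assumed counts and do not forecast a bias. The conclusion assumes that at least some sites apply the exclusion as written. It is worth correcting because it touches a primary objective and costs very little. No figure in the plan changes, and the efficacy analysis is not involved.

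**What to change.** Reconcile 7.1.1 with 7.1.6 and 7.2. Replace the whole bullet with: *Any laboratory abnormality that does not meet the criteria in Section 7.1.6.* Section 7.1.6 then decides AE status, and cause is recorded only in the relationship field.

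Deleting just the half about other conditions would not be enough. The remaining half, on non-significant findings, could still exclude an abnormality that meets another 7.1.6 criterion, such as needing diagnostic tests.

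SAP 9.1 needs no change, since it already carries the definition without exclusions. The cost is one edited bullet and a few more AE entries, mostly classed as not related. No laboratory output and no 7.3.2 trigger changes.
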